4.1.1.4 Multiple Imputation (MI)

Missing pre-specified categorical and continuous efficacy data will be imputed with MI under Missing at Random (MAR) assumption using the ITT population (Enders, 2010). MI method will be applied on the data of a given endpoint that are assumed to be MAR.

The current assumption on which the primary analysis is based is that all subjects with a missing response at a given timepoint and/or with missing responses after treatment withdrawal are regarded as non-responder, non-response is assumed regardless of whether the subject responded to the treatment at the time of the drop-out. The secondary analyses using LOCF approach assume that all subjects with missing data at a given timepoint and/or after treatment withdrawal maintain their last observed assessment over time.

MI under MAR assumption assumes that dropouts behave similarly to other subjects in the same treatment group who did not withdraw and continued to be treated with the study treatment. In terms of efficacy, this will estimate the effect of treatment as if all subjects were treated as randomized.

MI will be implemented in three steps using SAS[®], version 9.4 or higher (see Figure 4.1.). Depending on the nature of data, some of the steps may have some specificities (Demirtas et al., 2008). MI method assumes a multivariate normal distribution for the continuous variable of interest (e.g. PASI percent change) at each visit.

4.1.1.4.1 Step 1: Imputation Phase

1.a. Initialization

Create a dataset with only one record per subject containing all scheduled assessments at each visit including the baseline assessment, the planned treatment group and all covariates of the imputation model to use SAS[®] PROC MI. The covariates of the imputation model will be the stratification factors as randomized at the least. Other covariates such as sites, gender may be considered to be added.

1.b. Exploration of the Missing Data Pattern

Check the pattern of missing data. The pattern of missing data may be intermittent or non-monotone, i.e. that a subject may miss an assessment at a planned visit and may return for assessment at the subsequent visits before study completion or treatment withdrawal. That will be the assumption by default. However, the pattern might be monotone for shorter periods such as the induction period up to Week 12 i.e. no subjects miss a scheduled visit before withdrawing treatment or completing the period.

If the pattern for the considered period is intermittent, please go to Step 1.c. Otherwise, go to Step 1.d.

1.c. Partial Imputation of intermittent Missing Data

Generate n datasets with a monotone missing pattern using a Markov Chain Monte Carlo (MCMC) method with one single chain, 1000 burn-in iterations at least, and a non-informative Jeffreys prior for each treatment group. The model will include weight category and prior use of biologic therapy stratum derived from the observed values (actual stratum), the baseline and post-baseline assessments. Each intermittent missing value will be imputed using independent samples that are generated by MCMC from the posterior distribution.

The chosen n will be 100 imputed datasets at least. A larger number for n such as 500 or 1000 might be considered depending on the computational cost. If the baseline assessment was missing, the baseline will be imputed at this step.

1.d. Imputation of Monotone Missing Data

Impute the monotone missing data using a Bayesian framework for each treatment group. The model will include the explanatory variables of actual weight and prior use of biologic therapy stratum, the assessment at baseline and the assessments at all visits. If step 1.c. was skipped, the n datasets will be generated at that stage.

No rounding or range restrictions will be applied to imputed values during Steps 1.c and 1.d (Horton et al., 2003). The imputation (Steps 1.c and/or 1.d) will be run multiple times with different random seeds to ensure that the imputation model convergence was reached.

[figure not shown]

Figure 4.1: Multiple Imputation Process when Imputing n Datasets

4.1.1.4.2 Step 2: Analysis Phase

Analyze the n imputed datasets separately using a Cochran-Mantel-Haenszel (CMH) analysis for the binary variables and an ANCOVA for the continuous variables.

2.a. Binary Variables

The analysis model and the displayed statistics will be identical to those described for the primary or secondary analyses (refer to Sections 4.2.1.3 and 4.2.2.2.1 for further details). Briefly, a CMH analysis with the actual weight category and prior use of biologic therapy stratum as the stratification factors will be performed for each imputed dataset yielding n common CMH ORs with their 95% CI and n p-values for each pairwise treatment comparison at a given visit where applicable.

2.b. Continuous Variables

Treatment comparisons will be made for each imputed dataset using an ANCOVA model including planned treatment group, actual weight category and prior use of biologic therapy stratum as factors and the baseline value as a covariate in the model as described in Section 4.2.2.2.3. The Least-Squares Means (LSM) along with the SE and 95% CI for each treatment group and the differences in LSM for each pairwise treatment comparison, their associated SE, 95% CI and p-value will be computed for the n datasets at the specified visits.

4.1.1.4.3 Step 3: Pooling Phase

The analysis results from the n imputed datasets will be combined into an overall result for each treatment comparison and visit using SAS[®] PROC MIANALYZE.

3.a. Binary Variables

Rubin's rules for combining results from multiple imputed datasets are based on the assumption that the statistics estimated from each imputed dataset are normally distributed (Rubin D., 1976). Therefore, estimates of ORs that follow a log normal distribution will be pooled after using a log transformation. Similarly, a Wilson-Hilferty transformation will be applied before combining the p-values given that the CMH test is based on a chi-square distributed statistic (Ratitch, B., Lipkovich, I. & O'Kelly, M., 2013).

3.b. Continuous Variables

The LSM along with the SE and 95% CI and the differences in LSM, their associated SE, 95% CI and p-value for each treatment comparison will be combined using Rubin's rule (Rubin D., 1976).

4.1.1.5 Tipping Point Analysis

The tipping point analysis will only be performed on the primary analysis. It will test the null hypotheses of no treatment effect vs. placebo at Week 12 for the primary endpoint (IGA score of 0 or 1 at Week 12, with an IGA reduction from baseline of at least 2 points) as specified in Section 4.2.1.3 for a range of deviations from Missing At Random (MAR) assumption for the control group and the active treatment groups independently. It will include scenarios where the dropout on active treatment has worse outcomes than dropouts on the placebo group.

The purpose of the tipping point analysis is to assess how severe a departure from MAR has to be to overturn the conclusions drawn from the primary analysis. If the departures from MAR assumption to change the statistical significance (evidence of treatment effect) to statistical insignificance (no evidence of treatment effect) are deemed implausible, the tipping point analysis will give supportive evidence to the primary objective under Missing Not At Random (MNAR) assumption (Liublinska, V. and Rubin, D.B., 2014).

4.1.1.5.1 Step 1: Imputation Phase

1.a. Initialization

Create n copies of the analysis dataset and combine these datasets. The analysis dataset should be identical in structure and content to the dataset created for MI (refer to Section 4.1.1.4.1).

1.b. Imputation

For any active or control treatment group, different response probabilities (e.g. 0%, 20%, 40% 60%, 80% and 100%) will be applied successively to impute the missing values of IGA response at Week 12 and similarly for the placebo group. Missing IGA responses at Week 12 will be randomly imputed with 0 (i.e. non-responder) and 1 (i.e. responder) with the chosen response probabilities. The different steps below will be described with the aforementioned response probabilities provided as an example: 0%, 20%, 40% 60%, 80% and 100%.

This imputation will be performed by generating random numbers from a Bernoulli distribution to perform the imputation on the missing IGA responses at Week 12 in two steps:

- i. Impute the missing values of the placebo group by generating random numbers from a Bernoulli distribution using a response probability of 0% for example.
- ii. Impute the active/control treatment groups with the same methodology using a response probability of 20% for example.

4.1.1.5.2 Step 2: Analysis Phase

Analyze the n imputed datasets separately using a CMH analysis as described in Section 4.1.1.4.2.

4.1.1.5.3 Step 3: Pooling Phase

The analysis results from the n imputed datasets will be combined into an overall result for each treatment comparison and visit using SAS[®] PROC MIANALYZE as described in Section 4.1.1.4.3 - binary variables.

4.1.1.5.4 Step 4: Repetition Phase

Return to Step 1 using the next combination of response probability for the missing IGA response at Week 12: 0% for the placebo group and 40% for the active/control treatment group (0/0.4) and so forth.

For the following response probability combinations 0/0, 0/1, 1/0, 1/1, missing data will be imputed using one single dataset and analyzed as described in Section 4.1.1.4.2.

4.2 Efficacy

4.2.1 Primary Analysis

The primary objective is to assess the efficacy of four dose regimens of M1095 versus placebo on IGA score in subjects with moderate to severe chronic plaque-type psoriasis at Week 12.

All subjects within the ITT population will be included in the primary efficacy analysis.

4.2.1.1 Variable

The primary variable is the response rate for the IGA score at Week 12, which is defined as the proportion of subjects who achieve an IGA score of 0 or 1 at Week 12 and with an IGA reduction from baseline of 2 points or more at Week 12. This variable will be denoted by “IGA response” in subsequent sections.

Baseline IGA score is defined as the last non-missing IGA score prior to the first dose of study medication.

IGA response for subjects with missing baseline and/or Week 12 IGA score will be imputed using NRI approach. NRI consists in imputing any missing IGA score response as a non-response (see Section 4.1.1.2 for further information).

4.2.1.2 Descriptive Analyses

Descriptive summary of the proportion of subjects achieving the primary endpoint will be tabulated by treatment group and also by treatment group and actual stratum (≤ 90 kg and prior biologic use, ≤ 90 kg and no prior biologic use, > 90 kg and prior biologic use, > 90 kg and no prior biologic use) i.e. derived from the observed values of body weight and prior biologic use for all visits up to Week 12. Summary statistics will include the number and percentage of subjects achieving an IGA response for all visits up to Week 12.

The 95% confidence intervals of the binomial proportions will be estimated using the Clopper-Pearson exact interval.

The primary variable will also be listed by treatment group, subject and visit.

Bar plots of IGA responder rates (95% CI) by treatment group overall and for each stratum will be created.

4.2.1.3 Inferential Analyses

The IGA responder rates at Week 12 will be compared between treatment groups using CMH test stratified by actual prior use of biologic therapy (yes/no) and body weight stratum (≤ 90 kg, > 90 kg) as observed at baseline. The following four null hypotheses will be individually tested at the unadjusted two-sided 5% significance level:

- H₁: M1095 30 mg Q2W × 3, followed by 30 mg Q4W × 1, is not different from placebo with respect to achievement of IGA response,
- H₂: M1095 60 mg Q2W × 3, followed by 60 mg Q4W × 1, is not different from placebo with respect to achievement of IGA response,
- H₃: M1095 120 mg Q2W × 3, followed by 120 mg Q4W × 1, is not different from placebo with respect to achievement of IGA response,
- H₄: M1095 120 mg Q2W × 6 is not different from placebo with respect to achievement of IGA response

resulting in the following comparisons at Week 12 between the treatment groups/regimens:

- | | | |
|---|---|---|
| 
 • M1095 30 mg wk 0, 2, 4, 8 • M1095 60 mg wk 0, 2, 4, 8 • M1095 120 mg wk 0, 2, 4, 8 • M1095 120 mg wk 0, 2, 4, 6, 8, 10 | } | vs. placebo wk 0, 1, 2, 3, 4, 6, 8, 10. |
|---|---|---|

The CMH Odds Ratio (OR) for the comparison of each M1095 treatment arm to placebo will be presented along with its 95% CI and associated p-value.

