## 4.0 STUDY DESIGN

### 4.1 Overall Design

This is a multi-center phase 2b study in subjects with moderate to severe chronic plaque-type psoriasis. Approximately 300 subjects will be enrolled at approximately 60 investigator sites in North America and Europe. The study will consist of a 4-week screening period (Week -4 to Week 0), a 12 week treatment period which is placebo-controlled (Week 0 to Week 12), a 12 week maintenance/escalation period where all subjects are on active treatment (Week 12 to Week 24), a 24 week response assessment/dose hold period where active treatment is withheld if subjects being treated with M1095 have an IGA score of 0 at the beginning of the period (Week 24 to Week 48) and a final assessment period for safety follow up (Week 48 to Week 52). The study will be double-blind up to Week 24, with subject- and investigator-blind maintained throughout.

Subjects will be randomized in a 1:1:1:1:1:1 ratio, with approximately 50 subjects randomized into each of six treatment groups as shown below and in Figure 1:

1. Placebo wk 0, 1, 2, 3, 4, 6, 8, 10 / M1095 120mg wk 12, 14, 16 and q4w.
2. M1095 30mg wk 0, 2, 4, 8, 12 and q4w.
3. M1095 60mg wk 0, 2, 4, 8, 12 and q4w.
4. M1095 120mg wk 0, 2, 4, 8, 12 and q8w.
5. M1095 120mg wk 0, 2, 4, 6, 8, 10, 12 and q4w.
6. Secukinumab 300mg wk 0, 1, 2, 3, 4, 8, 12 and q4w.

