## 9.2 Sample Size Determination

A sufficient number of subjects will be screened, so that a total of approximately 300 subjects will be randomized (approximately 50 per treatment group.)

With this sample size, the study has >99% power to detect a statistically significant difference between any treatment arm and placebo in the IGA score of 0 or 1 rate at Week 12, with a two-sided, unadjusted type I error of 0.05. These calculations assume IGA score of 0 or 1 rates of >88% for study drug and ≤7% for placebo. As this is a phase 2 study, there will be no adjustments for multiplicity.

Exploratory analyses between the different dose levels of M1095 will also be performed. The PASI 100 response rate offers more discriminatory potential for this. Phase 1 data and response simulations give a PASI 100 response rate at Week 12 varying from 45 to 72%. With the sample size of 50 subjects per group, based on these assumed PASI 100 response rates at Week 12, the comparison between the highest and lowest M1095 doses has approximately 79% power.

Power calculations have been performed with SAS v.9.4 Proc Power using the methodology for a two-group chi square test of equal proportions.

Randomization will be stratified by prior biologic use (yes, no) and weight (≤90kg, >90kg).

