4.2.2.2 Descriptive and Inferential Analyses

4.2.2.2.1 Binary and Categorical Variables

The proportions of the binary variables will be summarized by treatment group at each visit up to Week 52. Pairwise comparisons vs. placebo and pairwise comparisons across M1095 treatment arms will be made at each visit up to Week 12 and at Weeks 24, 36 and 48 using the CMH test of 2-by-2 tables stratified by actual prior use of biologics (yes/no) and body weight stratum (≤ 90 kg, > 90 kg) in the same way as for the primary analysis (please refer to Section 4.2.1.3). No formal statistical testing will be performed between M1095 treatment arms and Secukinumab as the Secukinumab arm is for reference only. However, Secukinumab will be compared to placebo using the same methodology. In case of a large number of stratification errors, the key secondary analyses might be repeated as described in Section 4.2.1.3 but using the per randomized stratum as entered into the IRT system by the sites.

The assumption of homogeneity of association between treatment and the binary variables in the different actual strata will be tested at Weeks 12, 24, 36 and 48 for all pairwise comparisons M1095 vs. placebo at 10% significance level using the Breslow-Day test as explained in Section 4.2.1.4.

For the categorical analyses, the proportion and number of subjects in each IGA category at a given visit from baseline will be presented by treatment group and over time at each visit up to Week 12 for the induction period, from Week 12 to Week 24 for the maintenance/escalation period and from Week 24 to Week 48 for the response assessment/dose hold period.

Bar plots and line plots of the responder rates with 95% CI will be provided by treatment group and over time up to Week 48 overall.

The binary secondary efficacy variables will be listed by treatment group and over time.

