4.12.2.3 Safety Variables

The number and percentage of subjects with AESI will be summarized by treatment group classed by SOC and PT for each category of the subgroup for the induction and overall period (refer to Section 4.9.2.5).

REDACTED COPY

This document must not be used to support any marketing authorization application or any variation or extension of such application

5 Sample Size Calculation

A sufficient number of subjects will be screened, so that a total of approximately 300 subjects will be randomized (approximately 50 per treatment group).

With this sample size, the study has > 99% power to detect a statistically significant difference between any treatment arm and placebo in the IGA score of 0 or 1 rate at Week 12, with a two-sided, unadjusted type I error of 0.05. These calculations assume IGA score of 0 or 1 rates of > 88% for study drug and \leq 7% for placebo. As this is a phase 2 study, there will be no adjustments for multiplicity.

Exploratory analyses between the different dose levels of M1095 will also be performed. The PASI 100 response rate offers more discriminatory potential for this. Phase 1 data and response simulations give a PASI 100 response rate at Week 12 varying from 45 to 72%. With the sample size of 50 subjects per group, based on these assumed PASI 100 response rates at Week 12, the comparison between the highest and lowest M1095 doses has approximately 79% power.

Power calculations have been performed with SAS v.9.4 Proc Power using the methodology for a two-group chi square test of equal proportions.

Randomization will be stratified by prior biologic use (yes, no) and weight (\leq 90 kg, > 90 kg).

6 Reference List

Abraha, Iosief & Montedori, Alessandro. (2010). Modified intention to treat reporting in randomised controlled trials: Systematic review. *BMJ (Clinical research ed.)*. 340. c2697. 10.1136/bmj.c2697.

Committee for Medicinal Products for Human Use, 2017. Guideline on immunogenicity assessment of therapeutic proteins. London: European Medicines Agency.

Committee for Proprietary Medicinal Products (CPMP), Points to Consider on Adjustment for Baseline Covariates (2003). *Stat Med*, 23(5), pp.701-709.

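### The primary analysis plans only a CMH odds ratio versus placebo as its effect estimate and has no fallback if it is infinite; at the planning rates at least one of the four would be infinite in about 13–20% of trials

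*SAP*

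**What the plan says.** SAP 4.2.1.3 compares each of the four M1095 regimens with placebo at Week 12 by a CMH test over four strata (prior biologic use by weight at 90 kg). For the size of the effect it says: "The CMH Odds Ratio (OR) for the comparison of each M1095 treatment arm to placebo will be presented along with its 95% CI", together with the p-value. SAP 4.2.1.2 adds responder rates by arm and by stratum, with Clopper-Pearson intervals for the proportions, but no difference between arms. Protocol 9.4.1 names the test and no effect measure.

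The planning assumptions are in Protocol 9.2, repeated in SAP Section 5: "rates of >88% for study drug and ≤7% for placebo", about 50 subjects per arm, "with a two-sided, unadjusted type I error of 0.05". Allocation is equal over six arms (Protocol 4.1).

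Two other places depend on the same estimator. SAP 4.2.2.2.1 analyses the binary secondary endpoints "in the same way as for the primary analysis (please refer to Section 4.2.1.3"). SAP 4.1.1.4.3 combines multiply imputed results as follows: "estimates of ORs that follow a log normal distribution will be pooled after using a log transformation"; the tipping-point analysis in 4.1.1.5.3 refers back to that step.

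Neither document says what to report if the odds ratio cannot be computed. There is no exact method, no continuity correction and no risk difference for the primary endpoint. SAP 4.2.2 does name a difference in response proportions as the estimand, but only for Weeks 24, 36 and 48.

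**The concern.** A common odds ratio needs events in both sparse cells of the same stratum. At the planning rates an arm of 50 is expected to have 50 × 0.12 = 6 M1095 non-responders and 50 × 0.07 = 3.5 placebo responders, and each group is spread over four strata. These counts are the least favourable end of the sponsor's assumption, because the rates are stated as bounds. Protocol 2.3 reports phase 1 rates of 88% to 100% for clear or almost clear on a similar scale (sPGA).

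If no stratum holds both kinds of subject, that regimen has a p-value but no estimate of effect with a confidence interval for the primary endpoint. Any substitute would then be chosen after the counts are known. One placebo arm serves all four comparisons, so a single sparse placebo arm can affect several of them at once.

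**Working it through.** **1. Reproduce the plan's power.** For the two-group chi-square test with n = 50 per arm, power = Φ{[|p1 − p2|√n − 1.96√(2p̄(1 − p̄))] / √(p1q1 + p2q2)}.

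- PASI 100, 45% vs 72%: (1.909 − 1.366)/0.670 = 0.81, so power is 79.1%. The plan states about 79%.
- IGA 0/1, 88% vs 7%: (5.728 − 1.384)/0.413 = 10.5, so power exceeds 99.9%. The plan states above 99%.

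Both figures reproduce.

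**2. Condition for an infinite odds ratio.** The Mantel-Haenszel estimate is Σ(a·d/n) / Σ(b·c/n), where a and b are M1095 responders and non-responders, and c and d are placebo responders and non-responders. The denominator is zero exactly when no stratum has both b > 0 and c > 0. For fixed stratum sizes n per arm,

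P(infinite) = Π over strata of [1 − (1 − pA^n)(1 − (1 − pP)^n)].

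**3. At 88% vs 7%.** With strata of 13, 13, 12 and 12 per arm:

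- size 13: (1 − 0.88^13)(1 − 0.93^13) = 0.495
- size 12: (1 − 0.88^12)(1 − 0.93^12) = 0.456
- P(infinite) = 0.505² × 0.544² = 0.076

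Stratum shares are not in the documents. With prior biologic use at 30%, 20% or 15% and weight split evenly, the result is 0.070, 0.063 or 0.059. Without stratification it would be 1 − (1 − 0.88^50)(1 − 0.93^50) = 0.028, so stratifying roughly doubles the risk or more.

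**4. Four comparisons sharing one placebo arm.** Simulation, 40,000 trials per scenario, with random stratum sizes under three assumed mixes: equal; 30% prior biologic × 45% above 90 kg; 15% × 45%. Missing subjects count as non-responders, as SAP 4.2.1.1 requires, so both rates are multiplied by one minus the missing fraction. No dropout rate is documented; 5% and 10% are assumptions.

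| M1095 vs placebo | Missing | Infinite, per comparison | At least one of four |
|---|---|---|---|
| All 88% vs 7% | 0% | 6–8% | 13–20% |
| | 5% | 5–6% | 9–13% |
| | 10% | 5–6% | 7–10% |
| 88/90/92/95% vs 7% | 0% | varies by arm | 31–40% |
| | 5% | varies by arm | 13–20% |
| | 10% | varies by arm | 9–13% |
| All 95% vs 7% | 0% | 21–27% | 53–64% |
| | 5% | 9–12% | 21–30% |
| | 10% | 7–8% | 12–17% |

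**5. Precision when finite.** The true odds ratio at 88% vs 7% is (0.88/0.12)/(0.07/0.93) = 97. Among finite simulated estimates with no missing data, the median is about 105 and the median lower and upper 95% limits (Robins-Breslow-Greenland variance) are about 21 and 510.

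**6. Risk difference at the same rates.** 0.88 − 0.07 = 0.81; SE = √(0.1056/50 + 0.0651/50) = 0.058; approximate 95% CI 0.81 ± 1.96 × 0.058, or 70 to 92 points. This is the unstratified form. The stratified estimate needs no particular cell to be filled, only both arms in at least one stratum.

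**The case against.** The strongest reply is that the problem is uncommon at the stated figures and costs little when it occurs. At 88% vs 7% the odds ratio is finite in at least 92% of comparisons. Non-responder imputation adds M1095 non-responders and so lowers the risk; with all arms at 95%, an assumed 5% missing roughly halves it or better. The CMH test does not need a finite odds ratio. The rates by arm are tabulated, and with a contrast this large the effect will be plain from them; an unstratified difference can be worked out from the counts. All of this stands. It limits the point to estimation but does not supply the missing estimate. If the planning rates are read as already counting missing subjects as failures, the 0% rows apply.

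Some stronger readings are tempting and are not supported:

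- *The odds ratio will often be infinite at the planning rates.* The calculation gives 6–8% per comparison. Larger figures need response better than the bounds, which the inequality signs permit but which is not the stated case.
- *Regimens cannot be compared because their odds ratios against placebo are unstable.* SAP 4.2.2.2.1 compares the M1095 arms with each other directly, so placebo sparsity does not enter.
- *PASI 100 versus placebo fares far worse.* This is plausible, but neither document gives a placebo PASI rate, so any figure would rest on an assumed one.
- *The multiple-imputation and tipping-point analyses fail.* Both are optional in Table 4.4, and their p-values are pooled separately through a Wilson-Hilferty transformation. Only the pooled odds ratio is exposed.

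**Conclusion.** The point holds as a gap in estimation with a modest but real probability. It rests on 50 per arm, four strata with assumed shares, equal response rates across strata, and the planning bounds taken at face value. On that basis, about one trial in five to one in eight would lack a finite odds ratio for at least one primary comparison, or roughly 7–13% of trials with 5–10% missing. Response above the bounds raises this: with all arms at 95% vs 7% it is 53–64%, or 12–30% with 5–10% missing.

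A reader might infer that the primary tests or the sample size are in doubt. They are not: the four hypothesis tests and the stated power stand. A prespecified risk difference is worth adding because it is cheap, estimable whatever the sparse cells contain, and of the same kind as the estimand SAP 4.2.2 already uses for later visits. Replacing the odds ratio altogether would be a matter of preference, and the documents give no reason to require it.

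**What to change.** - In SAP 4.2.1.3, and by reference in 4.2.2.2.1, keep the stratified CMH test for the p-value. Add the stratified Mantel-Haenszel difference in response proportions with a 95% CI, naming the method (for example Sato variance or stratified Newcombe).
- Report the CMH odds ratio alongside it when finite, and state that it is *not estimable* otherwise.
- In SAP 4.1.1.4.3, if the optional multiple-imputation or tipping-point analyses are run, pool the risk difference by Rubin's rules, so that an infinite odds ratio in one imputed dataset does not break the pooled estimate.

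The cost is SAP wording, one more effect measure in the tables and a small amount of programming. The p-values and sample size do not change. The rule should be fixed before the analysis team sees results by treatment, since a substitute chosen afterwards would be post hoc.
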